7.7. Definition of End of Study

The end of the study is defined as the date of the last follow-up telephone call to the last participant recruited. Any planned formal analyses of the data will take place after this time point.

8. WARMING METHOD and TEMPERATURE MONITORING

The participants recruited to this study will all undergo hemiarthroplasty. During their surgery the patient will be kept warm as part of their standard care. The primary method used will be either Forced Air Warming (FAW) or direct contact Resistive Fabric Warming (RFW) depending on the randomisation arm to which they have been allocated. Both FAW and RFW are established and licensed for use in the UK and are equally effective at preventing inadvertent perioperative hypothermia (Negishi et al.2003). The warming devices will be used in accordance with national guidelines as defined in NICE CG65. Where necessary for optimal clinical care, additional warming methods can be employed at the discretion of the supervising clinician. Standard clinical care would normally include actively warming intravenous fluids and blood products in all patients.

Temperature will be monitored throughout the surgical procedure at all recruiting sites. All thermometers will be calibrated according to the standard protocol at each site. Where possible, site will use the 'SpotOn zfd' temperature monitoring system provided by the company 3MTM (Patient Warming Solutions).

As part of standard clinical care the patient's temperature will be measured and documented before induction of anaesthesia and every 30 minutes until the end of surgery. For the binary analysis, IPH will be defined as a temperature of <36°C at the end of surgery.

In addition, we will use the SpotOn zfd to log a continuous readout to provide the following data:

- a) IPH at any time during surgery and at the end of surgery/arrival in the recovery room
- b) Area under the curve for total hypothermia time during surgery
- c) Weighted hypothermia time (i.e. time spent at 35.5°C is more significant than time spent at 35.9°C)

9. SAFETY REPORTING

A serious adverse event is defined as any untoward medical occurrence that:

- results in death OR
- is life-threatening OR
- requires inpatient hospitalisation or prolongation of existing hospitalisation OR
- results in persistent or significant disability/incapacity

Other 'important medical events' may also be considered serious if they jeopardise the participant or require an intervention to prevent one of the above consequences.

NOTE: The term "life-threatening" in the definition of SAE refers to an event in which the participant was at risk of death at the time of the event; it does not refer to an event which hypothetically might have caused death if it were more severe.

9.1. Reporting Procedures for Serious Adverse Events

All SAEs will be recorded in the CRF. An SAE occurring to a participant will be reported to the sponsor, the Data and Safety Monitoring Board (DSMB) (see section 12) and the REC when, in the opinion of the Chief Investigator, the SAE is **unexpected** and **related** to the allocated intraoperative warming technology. Such SAEs will be reported using the sponsor's SAE report form and emailed to [contact] within 24 hrs of becoming aware of the event. If required, the SAE will be reported to the appropriate bodies within 15 days of the CI becoming aware of the event.

The following will be considered as expected SAE's:

- 1) Complications of hip fracture and hip fracture surgery (including anaesthesia)
- 2) Complications arising as a result of inadvertent perioperative hypothermia
- 3) Heat necrosis and pressure areas acquired during the clinical episode relevant to the study

4) Inter-current illnesses causally related to comorbid conditions that the investigator believes are likely given the patient's history, age and other factors

The investigators will use their judgement, such that SAEs technically meeting the definitions above but that seem unexpected in terms of severity, duration or other factors may be regarded as unexpected. All participants experiencing SAEs will be followed-up as per protocol until the end of the trial.

Documented endpoints, including superficial or deep SSI and IPH (but excluding death), will not be reported as SAEs.

10. STATISTICS AND ANALYSIS

10.1. Pilot study

The primary objective of the pilot study is to inform accrual expectations and data management strategies for a definitive trial. A formal interim analysis of efficacy will only be invoked if recruitment to the pilot study exceeds 1000 patients. This will be the responsibility of an independent statistician.

Outcome data (including SAEs) and compliance will be summarised according to the randomised intervention. Measures will be quantified and, where appropriate, a 95% confidence intervals will be presented. No imputation for missing data will be performed for the pilot study.

Estimates of recruitment rates, and the rates of definitive deep surgical site infection within 90 days of surgery, will be used to further inform any changes to design, data management and recruitment strategy for the main study.

The DSMB will review interim summaries for accrual, safety, conduct and, if appropriate, outcome. In the light of the data presented, and any additional information that they require, the DSMB may recommend amendment, suspension or closure of the study to the Trial Steering Committee (TSC).

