The biggest barrier to a successful funding application for this trial is the number of participants required. Hemiarthroplasty carries a risk of deep SSI of around 2.5%. To provide 90% power to demonstrate an absolute risk reduction of 1%, using a 5% significance level, a trial will need to recruit approximately 8630 participants over a 3-year period. To ensure a robust application, we will conduct a pilot study across a limited number of NHS sites to demonstrate that the recruitment strategy, randomisation process and follow-up assessments are appropriate and effective. Provided that no major strategic changes are required, we anticipate that refinements can be adopted and the study rolled out to additional centres without a prolonged break in recruitment at pilot centres. Pilot data will subsequently be transferred to the full trial and will contribute to the final analysis.

The United Kingdom Clinical Infection Research Group (UKCIRG) is a research collaboration consisting of 43 NHS trusts in the UK. Its current interventional trials include The OVIVA Study (Oral vs. Intravenous Antibiotics in bone and joint infection) which recruits at 27 centres, and the ARREST Trial (Adjunctive Rifampicin to Reduce Early mortality in Staph aureus bacteraemia) which recruits at 30 centres. The WHITE cohort is a collaboration of 16 NHS trusts recruiting patients under a single comprehensive treatment pathway, based upon the NICE Hip Fracture Guidelines, and provides core outcome measurements collected within the framework of the UK National Hip Fracture Database. Assuming that 30 of the centres from these networks are willing to participate, progression from pilot to a definitive trial will be considered if recruitment at each pilot centre exceeds an average of 2 participants per week or projects to over 100 per year after six months of activity. A second progression target designed to assess data management strategy will be defined by follow-up data for primary endpoints at Day 30 being available for >90% of participants six months after the start of the pilot study.

4. **OBJECTIVES AND OUTCOME MEASURES**

[figure not shown]
- **Primary Objective** The primary objective of the RIIiO pilot study is to inform and assess the recruitment and data management strategies for a full trial.
- **Secondary Objectives** The secondary objective of the pilot study is to confirm the methodology for health economic evaluation in the context of the full trial.

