10.3. Analysis of Outcome Measures for the full trial

Pending recommendations arising from the pilot study, we assume that the analysis of outcome measures for the full trial will take the following form:

Analysis of the primary endpoint:

Based on the ITT population (i.e. participants analysed according to their allocated trial arm, regardless of their compliance with the protocol), the proportions of participants in either treatment arm experiencing a definitive deep surgical site infection within 90 days from surgery will be calculated.

We will determine the superiority of either of the two trial interventions by assessing if there is a statistically significant difference in the log-odds of infection between the randomised treatment arms using a logistic regression model with randomised treatment as a fixed effect; superiority of either intervention is defined by the treatment coefficient being statistically significant at the 5% level. Covariates considered *a priori* to be prognostic of outcome may be included to give an adjusted odds ratio. These would be agreed by consensus and written into the full statistical analysis plan and signed off prior to analysis of unblinded data.

Secondary analyses will include a per protocol analysis based on all participants who have received their randomised intervention. A survival analysis will be performed to assess potential differences in the time to diagnosis of definitive deep surgical site infections. Health economic evaluation will be conducted by a dedicated health economist based on capital, maintenance and treatment costs, as well as EQ-5D-5L data, and will include the costs of complications.

Other secondary endpoint analyses will include regression models to calculate estimates of treatment differences for the primary and secondary outcomes unadjusted (primary analysis) and adjusted for age and co-morbidities (secondary analyses). These secondary analyses will focus on the consistency of point estimates and 95% confidence intervals rather than formal statistical significance testing.

Pre-defined subgroup analyses will use interaction tests to explore the consistency of treatment effects by trial site.

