13. QUALITY ASSURANCE PROCEDURES

The study will be conducted in accordance with the current approved protocol, International Conference on Harmonisation (ICH), Good Clinical Practice (GCP), relevant regulations and standard operating procedures. The trial sponsor will have full and free access to all aspects of the trial to allow monitoring of compliance with regulatory arrangements. A trial steering committee (TSC) will be formed that will comprise at least an independent chair person, an independent deputy chair, two independent public/patient group representatives, the Chief Investigator, Principal Investigators and the trial coordinator. The TSC will meet either in person or by teleconference at the beginning of the pilot study, after eight months of recruitment and towards the end of the pilot to (*i*) review protocol amendments and/or deviations, (*ii*) make recommendations regarding the conduct of the trial, (*iii*) review recruitment and follow-up rates, and (*iv*) assess the progression plan to a full trial based on extrapolation of data acquired in the pilot study.

A data and safety monitoring board (DSMB), comprising at least three independent and suitably qualified persons, will meet (either in person or by teleconference) to discuss the study design and SOPs shortly before the start of the study. Investigators will participate in this meeting. The DSMB will also meet prior to each TSC meeting and at any other time they deem necessary to evaluate patient safety and frequency of endpoints in an un-blinded analysis. Investigators will not be present. The DSMB may make recommendations to the TSC at any time during the pilot study and before investigators proceed with the multicentre trial.

If more than 1000 participants are recruited to the pilot study, a formal analysis of efficacy will be undertaken for presentation to the DSMB. It is expected that they would only recommend suspending the study if there was a very significantly worse outcome in one arm (e.g. using the Haybittle-Peto stopping boundary) or concerns around patient safety in relation to the trial.

Both intraoperative warming technologies are CE marked and will be used within the marketing authorisations. Therefore, the study does not fall within the remit of the Medicines for Healthcare products Regulatory Agency.

Monitoring of the study will be in accordance with a risk assessment and monitoring plan as implemented by the CTU.

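### Section 10.1 summarises pilot outcomes by arm without limiting who sees them, although the same participants are to be carried into a full trial that is still recruiting

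*Protocol*

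**What the plan says.** Section 10.1 of the protocol, on the pilot: "Outcome data (including SAEs) and compliance will be summarised according to the randomised intervention". Confidence intervals at 95% are added where appropriate. Recruitment rates and deep surgical site infection (SSI) rates "will be used to further inform any changes to design, data management and recruitment strategy for the main study"; the text does not say whether these infection rates are pooled or by arm.

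Section 3 (progression plan): "Pilot data will subsequently be transferred to the full trial and will contribute to the final analysis". It anticipates roll-out to more centres without a long gap in recruitment at the pilot sites.

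Section 10.3, on the full trial: "superiority of either intervention is defined by the treatment coefficient being statistically significant at the 5% level". Nothing there refers to a comparative pilot result that is already known.

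Two looks at comparative data are protected. Section 13 has the DSMB meet "to evaluate patient safety and frequency of endpoints in an un-blinded analysis. Investigators will not be present", and section 10.1 gives the formal efficacy analysis, triggered above 1000 participants, to an independent statistician. Neither provision mentions the by-arm summary at the end of the pilot.

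**The concern.** If pilot participants count in the final analysis, the pilot is the first part of the full trial. A by-arm outcome table at its end is then an interim comparative result. Section 7.7 places formal analyses after the last pilot follow-up call, which for the full trial is part-way through.

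The people who could see that table are those whose conduct can affect the rest of the data. Section 7.4 states that care teams and local study teams cannot be blinded. Section 7.6 has the local team make the follow-up calls and ask for clinical review where they think it necessary. Section 5 has the endpoint committee judge only the cases sent to it, and leaves secondary endpoints, including superficial SSI, to local investigators. Under section 13, the trial steering committee (TSC) that assesses progression includes the Chief Investigator and the Principal Investigators.

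That local staff know each patient's allocation is unavoidable. That they know which arm is ahead is avoidable. If they do, willingness to randomise, adherence to the allocated device and the effort spent looking for infections may drift differently in the two arms, and no later analysis can remove this.

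**Working it through.** **Inputs.** Deep SSI risk 2.5%, absolute reduction 1 point (so 1.5%), 90% power, 5% significance and about 8630 participants: section 3. Allocation 1:1: section 7.4. Pilot size: three centres with at least 100 each (section 7.1) gives 300. There is no upper limit, so 1000, the efficacy-analysis threshold, serves as an assumed upper case.

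**1. The plan's own figure.** With mean risk 0.02 and d = 0.01:
- n = [1.960·√(2·0.02·0.98) + 1.282·√(0.025·0.975 + 0.015·0.985)]² / 0.01² = 4116.8 per arm.
- With continuity correction: (n/4)·[1 + √(1 + 4/(n·d))]² = 4314.5, rounded up to 4315 per arm.
- Total 2 × 4315 = 8630. This matches the protocol with a two-sided 5% test.

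**2. How much the pilot can show.** The 95% half-width for the risk difference is 1.96·√(0.03915/n per arm), where 0.03915 = 0.025·0.975 + 0.015·0.985.

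| Pilot size | Share of 8630 | Expected deep SSIs (2.5% v 1.5%) | Half-width |
|---|---|---|---|
| 300 | 3.5% | 3.75 v 2.25 | 3.2 points |
| 1000 | 11.6% | 12.5 v 7.5 | 1.7 points |

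The effect sought is 1 point.

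**3. How often a 300-participant pilot misleads.** X and Y are independent binomial counts with 150 per arm; the probabilities are exact sums of P(X=x)·P(Y=y).
- Both risks 2.5%: P(larger ≥ 2 × smaller, larger > 0) = 0.457. Leaving out 1 v 0 changes this only to 0.453.
- Risks 2.5% and 1.5%: P(Y ≥ X) = 0.341.

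**4. Effect on the final 5% test.** Let t be the pilot share of 8630, so that final Z = √t·Z₁ + √(1−t)·Z₂.
- Final size and test unchanged by the by-arm result: type I error is exactly 5.0%.
- Worst case: after seeing Z₁, someone picks the final size as a multiple m of 8630 so as to maximise P(|√(t/m)·Z₁ + √(1−t/m)·Z₂| > 1.96). Averaged over Z₁, with m from 0.5 to 2, this gives 5.3% (pilot of 300) and 5.9% (pilot of 1000). With m from 1 to 2 it gives 5.1% and 5.3%.

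**5. Who is covered by a firewall.** Setting sections 10.1 and 13 side by side, the DSMB's closed review and the independent statistician's efficacy analysis are covered. The by-arm pilot summary has no named recipient and no embargo. Section 16 provides for open-access publications drafted with the investigators, and section 14.4 for a final report to the ethics committee and sponsor, with further reports, for example to a funder, on request.

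**The case against.** Several points on the other side are sound.

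- Progression does not depend on the arm difference. Section 3 ties it to recruitment (more than 2 a week, or over 100 a year) and to Day 30 primary-endpoint data for more than 90%. Section 13 lists recruitment and follow-up rates among the TSC's tasks, not by-arm infection.
- The deep SSI rate that informs the redesign may well be the pooled one. The synopsis speaks of an observed event rate, which suits sizing.
- Referral to the endpoint committee follows a rule: under section 5, any re-admission, clinic visit or return to theatre with signs or symptoms at the surgical site is a potential endpoint.
- The full trial is provisional and still needs funding.

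A reader might infer that the trial unblinds itself. It does not: it is open label by design, and the committee's blinding to individual allocation is untouched.

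A reader might also infer that the final 5% test is invalid. That would need a rule linking progression or size to the observed difference, and the protocol has none. If one assumed that the trial proceeds only when the pilot |Z| exceeds 1, the error rate among trials that proceed would be 5.6% (pilot of 300) to 7.0% (1000). The overall chance of a false positive would be 1.8% to 2.2%, because a trial that stops cannot reject.

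Nor does section 13 expressly reserve by-arm data for the DSMB; it only keeps investigators out of that review. The gap is therefore an omission in section 10.1, not a flat contradiction between sections.

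These points remove the error-rate argument. They do not supply a restriction on the by-arm summary, and a referral rule still depends on local staff noticing and reporting signs.

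**Conclusion.** The point holds as a cheap improvement. As written, the plan allows the aggregate by-arm outcome to reach unblinded staff who go on enrolling, treating and following patients in the trial that reuses those data. The harm is possible operational bias, whose size cannot be computed from the protocol. The type I cost is 5.0% under the stated rules and at most about 5.9% in the worst case considered.

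What would be released is also weak evidence: at 300 participants, a twofold imbalance arises by chance about 46% of the time, and the planned benefit is hidden or reversed about 34% of the time. These figures show that an early comparison would often mislead. They do not show that anyone would act on it.

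Assumptions: risks of 2.5% and 1.5% as planned, a pilot of 300 to 1000, a final size between 0.5 and 2 times plan in the worst case, and a full trial that goes ahead and includes the pilot participants.

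**What to change.** Amend section 10.1 to state that:

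1. The pilot report and the TSC receive deep SSI, superficial SSI and mortality rates for both arms combined, with 95% confidence intervals.
2. By-arm infection and mortality outcomes go only to the DSMB and the independent statistician until the full trial is analysed, or until it is decided that it will not proceed. Deaths are recorded as SAEs (section 9), so a by-arm SAE table must not disclose them.
3. Any resizing of the full trial uses the pooled event rate.
4. Recruitment and compliance may still be shown by arm.
5. If by-arm outcomes are released earlier, pilot participants are left out of the confirmatory test.

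Cost: a few sentences, and no by-arm infection results published at the end of the pilot if the full trial proceeds. The pilot's stated purpose, recruitment and data management, is not affected. Item 5 would be the expensive route: to keep 8630 in the confirmatory test, total recruitment becomes 8630 + 300 = 8930, or 8630 + 1000 = 9630.

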10.2. The Number of Participants

The primary objective of the pilot study is to demonstrate that strategies for recruitment and data management are appropriate and robust. There is, therefore, no defined upper limit for the number of participants required. The study will recruit at three sites initially, each of which performs between 4 and 8 hemiarthroplasties per week. Participants will be recruited over a minimum period of 12 months at each site and the number extrapolated to determine recruitment strategy, including expected number of sites, for a full trial.

10.3. Analysis of Outcome Measures for the full trial

Pending recommendations arising from the pilot study, we assume that the analysis of outcome measures for the full trial will take the following form:

Analysis of the primary endpoint:

Based on the ITT population (i.e. participants analysed according to their allocated trial arm, regardless of their compliance with the protocol), the proportions of participants in either treatment arm experiencing a definitive deep surgical site infection within 90 days from surgery will be calculated.

We will determine the superiority of either of the two trial interventions by assessing if there is a statistically significant difference in the log-odds of infection between the randomised treatment arms using a logistic regression model with randomised treatment as a fixed effect; superiority of either intervention is defined by the treatment coefficient being statistically significant at the 5% level. Covariates considered *a priori* to be prognostic of outcome may be included to give an adjusted odds ratio. These would be agreed by consensus and written into the full statistical analysis plan and signed off prior to analysis of unblinded data.

Secondary analyses will include a per protocol analysis based on all participants who have received their randomised intervention. A survival analysis will be performed to assess potential differences in the time to diagnosis of definitive deep surgical site infections. Health economic evaluation will be conducted by a dedicated health economist based on capital, maintenance and treatment costs, as well as EQ-5D-5L data, and will include the costs of complications.

Other secondary endpoint analyses will include regression models to calculate estimates of treatment differences for the primary and secondary outcomes unadjusted (primary analysis) and adjusted for age and co-morbidities (secondary analyses). These secondary analyses will focus on the consistency of point estimates and 95% confidence intervals rather than formal statistical significance testing.

Pre-defined subgroup analyses will use interaction tests to explore the consistency of treatment effects by trial site.

Patients who are randomised but, for whatever reason, do not proceed to surgical management will be excluded from all analyses. For patients who withdraw their consent, no further data will be collected from follow-up questionnaires, but data collected up to the point of withdrawal and routine data from medical records will be included unless the participant denies access to their medical records.

